1 OVERVIEW

Study Title: Leveraging interactive SMS messaging to monitor and support maternal health in Kenya

1.1 Home institution. Identify the institution through which the lead researcher listed on the IRB application will conduct the research. Provide any helpful explanatory information.

In general, the home institution is the institution (1) that provides the researcher's paycheck and that considers him/her to be a paid employee, or (2) at which the researcher is a matriculated student. Scholars, faculty, fellows, and students who are visiting the UW and who are the lead researcher: identify your home institution and describe the purpose and duration of your UW visit, as well as the UW department/center with which you are affiliated while at the UW.

Note that many UW clinical faculty members are paid employees of non-UW institutions.

The UW IRB provides IRB review and oversight for only those researchers who meet the criteria described in the [SOP Use of the UW IRB](#).

University of Washington

1.2 Consultation history. Has there been any consultation with someone at HSD about this study?

It is not necessary to obtain advance consultation. However, if advance consultation was obtained, answering this question will help ensure that the IRB is aware of and considers the advice and guidance provided in that consultation.

No

Yes → If yes, briefly describe the consultation: approximate date, with whom, and method (e.g., by email, phone call, in-person meeting).

1.3 Similar and/or related studies. Are there any related IRB applications that provide context for the proposed activities?

Examples of studies for which there is likely to be a related IRB application: Using samples or data collected by another study; recruiting subjects from a registry established by a colleague's research activity; conducting Phase 2 of a multi-part project, or conducting a continuation of another study; serving as the data coordinating center for a multi-site study that includes a UW site.

Providing this information (if relevant) may significantly improve the efficiency and consistency of the IRB's review.

No

Yes → If yes, briefly describe the other studies or applications and how they relate to the proposed activities. If the other applications were reviewed by the UW IRB, please also provide: the UW IRB number, the study title, and the lead researcher's name.

STUDY00006395 – similar procedures; Aim 3 of this application will be nested within 6395

STUDY00009531 – formative secondary data analysis in 9531 led to development of computational models that will be used in this application

1.4 Externally-imposed urgency or time deadlines. Are there any externally-imposed deadlines or urgency that affect the proposed activity?

HSD recognizes that everyone would like their IRB applications to be reviewed as quickly as possible. To ensure fairness, it is HSD policy to review applications in the order in which they are received. However, HSD will assign a higher priority to research with externally-imposed urgency that is beyond the control of the researcher. Researchers are encouraged to communicate as soon as possible with their HSD staff contact person when there is an urgent situation (in other words, before submitting the IRB application). Examples: a researcher plans to test an experimental vaccine that has just been developed for a newly emerging epidemic; a researcher has an unexpected opportunity to collect data from students when the end of the school year is only four weeks away.

HSD may ask for documentation of the externally-imposed urgency. A higher priority should not be requested to compensate for a researcher's failure to prepare an IRB application in a timely manner. Note that IRB review requires a certain minimum amount of time; without sufficient time, the IRB may not be able to review and approve an application by a deadline.

	No
	Yes

→ If yes, briefly describe the urgency or deadline as well as the reason for it.

1.5 Objectives Using lay language, describe the purpose, specific aims, or objectives that will be met by this specific project. If hypotheses are being tested, describe them. You will be asked to describe the specific procedures in a later section.

If this application involves the use of a HUD “humanitarian” device: describe whether the use is for “on-label” clinical patient care, “off-label” clinical patient care, and/or research (collecting safety and/or effectiveness data).

Our overarching aim is to implement a natural language processing (NLP) model into the previously developed Mobile WACH SMS platform and test its acceptability and impact on healthcare workers response time.

Aim 1: Validate performance of an NLP model trained to detect urgent client SMS.

Ten nurses from Mobile WACH studies will be presented with client messages from previous Mobile WACH studies, annotated with urgency predictions from the top 3 best performing NLP models. Each nurse will be asked to report their agreement with each prediction. The model with the highest sensitivity and specificity compared with the nurse “gold standard” determination will be selected for implementation in the Mobile WACH system.

Aim 2: Using a human-centered design approach, adapt the Mobile WACH system nurse interface to dynamically display urgent incoming messages.

Interactive focus groups will be conducted with 6-10 nurses from Mobile WACH studies and MOH facilities to collectively design a user interface that integrates real-time urgency classification of incoming messages and highlights messages classified as urgent.

Aim 3: Pilot the adapted Mobile WACH interface (AI-NEO) that identifies urgent client SMS and evaluate its acceptability and effect on nurse response time.

We will enroll 80 pregnant women to receive the AI-NEO SMS intervention. Women will be enrolled at 28-36 weeks gestation and will receive automated SMS regarding neonatal health from enrollment until 6 weeks postpartum, and will have the ability to interactively message with study nurses. Participant messages will be automatically categorized by urgency. We will evaluate intervention acceptability and recommended improvements among clients and nurses using quantitative and qualitative data collection at study exit (quantitative questionnaires with all client participants and qualitative interviews with 4 nurses). We will compare nurse response time to urgent and non-urgent participant messages with the ongoing Mobile WACH NEO trial, in which a non-adapted Mobile WACH system is used.

1.6 Study design. Provide a one-sentence description of the general study design and/or type of methodology.

Your answer will help HSD in assigning applications to reviewers and in managing workload. Examples: a longitudinal observational study; a double-blind, placebo-controlled randomized study; ethnographic interviews; web scraping from a convenience sample of blogs; medical record review; coordinating center for a multi-site study.

Mixed methods design phase followed by pilot longitudinal cohort study.

1.7 Intent. Check all the descriptors that apply to your activity. You must place an “X” in at least one box.

This question is essential for ensuring that your application is correctly reviewed. Please read each option carefully.

Descriptor

- 1. Class project or other activity whose purpose is to provide an educational experience for the researcher (for example, to learn about the process or methods of doing research).
- 2. Part of an institution, organization, or program’s own internal operational monitoring.
- 3. Improve the quality of service provided by a specific institution, organization, or program.
- 4. Designed to expand the knowledge base of a scientific discipline or other scholarly field of study, and produce results that:
 - Are expected to be applicable to a larger population beyond the site of data collection or the specific subjects studied, or
 - Are intended to be used to develop, test, or support theories, principles, and statements of relationships, or to inform policy beyond the study.
- 5. Focus directly on the specific individuals about whom the information or biospecimens are collected through oral history, journalism, biography, or historical scholarship activities, to provide an accurate and evidence-based portrayal of the individuals.
- 6. A quality improvement or program improvement activity conducted to improve the implementation (delivery or quality) of an accepted practice, or to collect data about the implementation of the practice for clinical, practical, or administrative purposes. This does not include the evaluation of the efficacy of different accepted practices, or a comparison of their efficacy.
- 7. Public health surveillance activities conducted, requested, or authorized by a public health authority for the sole purpose of identifying or investigating potential public health signals or timely awareness and priority setting during a situation that threatens public health.
- 8. Preliminary, exploratory, or research development activities (such as pilot and feasibility studies, or reliability/validation testing of a questionnaire)
- 9. Expanded access use of a drug or device not yet approved for this purpose
- 10. Use of a Humanitarian Use Device

11. Other. Explain:

[Empty orange-bordered box for explanation]

1.8 Background, experience, and preliminary work. Answer this question only if the proposed activity has one or more of the following characteristics. The purpose of this question is to provide the IRB with information that is relevant to its risk/benefit analysis.

- Involves more than minimal risk (physical or non-physical)
- Is a clinical trial, or
- Involves having the subjects use a drug, biological, botanical, nutritional supplement, or medical device.

“Minimal risk” means that the probability and magnitude of harm or discomfort anticipated in the research are not greater than those ordinarily encountered in daily life or during the performance of routine physical or psychological examinations or tests.

a. Background. Provide the rationale and the scientific or scholarly background for the proposed activity, based on existing literature (or clinical knowledge). Describe the gaps in current knowledge that the project is intended to address.

This should be a plain language description. Do not provide scholarly citations. Limit your answer to less than one page, or refer to an attached document with background information that is no more than three pages long.

Despite recent reductions in under-five mortality, neonatal mortality remains high.

The risk of a newborn dying depends significantly on where in the world they are born. Neonatal mortality rates (NMRs) vary substantially between countries from 1 to 44 per 1000 live births; almost 98% of neonatal deaths occur in low to middle income countries.¹ While the global NMR has fallen in recent decades, it still lags behind the impressive gains made for children 1 month to 5 years old. Between 1990 and 2016, under-5 mortality dropped by 62%, compared to 49% in neonates.² As a result, newborn deaths now account for a growing proportion of under-5 mortality. Moreover, many neonatal deaths occur at home and are therefore underreported. In Kenya, the NMR is 22.6 per 1000 live births,³ ranking among the countries with the highest number of neonatal deaths (~40,000 per year).² Siaya County in Western Kenya has a NMR of 27.3 per 1000 live births.⁴ National implementation of a free maternal health care policy and the resulting rise in facility deliveries have not had a significant impact on neonatal mortality.⁵ Achieving Sustainable Development Goal 3 of ≤12 neonatal deaths per 1000 live births by 2030 will require increased access to effective, evidence-based interventions that specifically address neonatal survival.⁶ Moreover, improving health during the critical neonatal period has the potential to not only support survival but also improve long-term developmental outcomes.⁷

Mobile health (mHealth) interventions can provide on-demand information and support families to improve maternal child health.

mHealth tools, which utilize mobile phones and other wireless technologies to support health, provide an attractive strategy to augment community-based care and connect households to CHV support more efficiently and frequently. More households in low-income countries own a mobile phone than have access to electricity or adequate sanitation.⁸ According to the Communications Authority of Kenya, there are now 46 million phone subscriptions in Kenya, for a national population of 43 million.⁹ **A World Bank report found that Kenyans living at the so-called economic “bottom of the pyramid” reported health information and communication was the service they most wanted to receive through their mobile phones.**¹⁰

Our collaborative team has developed an open-source human-computer hybrid SMS platform, Mobile WACH (Mobile Solutions for Women’s and Children’s Health).¹¹ Mobile WACH sends pre-composed messages to clients at scheduled times. Clients may send messages at any time; a live HCW answers incoming messages, leading to personalized dialogue. The internet-based HCW interface contains a dashboard designed to facilitate HCW management of tasks such as message response, patient tracking, and message translation into English. The system back-end collects SMS metadata such as time stamps and delivery status, as well as data on seminal events such as childbirth. To date, Mobile WACH has been implemented in 7 studies (including 4 randomized controlled trials, RCTs) targeting a range of reproductive, maternal, neonatal and child health outcomes. Scheduled intervention messages were developed for each study based on formative research with the target population,^{12–14} and behavioral theory selected based on the target outcome (Social Cognitive Theory,^{15,16} Theory of Planned Behavior,^{17,18} or Information-Motivation-Behavior Change Theory^{19,20}). All studies also allowed unstructured, personalized dialogue between clients and HCWs. **This suite of studies provides well-developed software and rich data (400,000 SMS) for the proposed project (Table 1).**

[figure not shown]
Table 1. Mobile WACH study summary

Study	Primary outcome	N clients	N SMS			Follow-up period
			Automated system	Personalized nurse	Client	
Mobile WACH XY RCT ¹⁷	Family planning	130	6,852 (144 unique)	3,356	3,577	Preg - 6mo
Mobile WACH Neo pilot (NEO Pilot) ²⁰	Neonatal health	799	26,021 (62 unique)	13,535	19,952	Preg - 3mo
Mobile WACH X RCT ¹⁶	HIV treatment adherence	276	39,993 (1149 unique)	6,361	10,122	Preg - 2yr
Mobile WACH Neo RCT (NEO RCT)	Neonatal health, Maternal depression	2,500	NA	NA	NA	Preg - 2mo

Automation may enable mHealth interventions to maximize efficiency and adaptability.

Figure. 1. Schematic of just-in-time adaptive intervention design

Adapted from Nahum-Shani et al.²⁷

The public health impact of mHealth interventions in resource-limited settings rests on their ability to achieve the following: (1) reach the people who most need support, (2) deliver efficacious treatment, and (3) reduce the burden on overstretched HCWs. Furthermore, there is increasing recognition that an mHealth intervention may be most efficacious if it is delivered *at the right time and adapts based on the context and response of individual clients*.²¹ This idea is articulated in the paradigm of just-in-time adaptive intervention (JITAI) design.^{22,23} Many mHealth interventions are inherently adaptive – particularly those that include dynamic interaction with a human. The JITAI paradigm

involves formalization of *when* and *how* the intervention should be adapted, by defining decision points, decision rules, and intervention options (Fig. 1). Implementation of this process can only feasibly be accomplished with **automatic, real-time processing of client data** (in the case of SMS interventions, unstructured natural language).^{22,24} **Table 2** summarizes the ways that automation can maximize mHealth intervention impact.

Natural language processing (NLP) enables computational analysis of unstructured language.

Table 2. Applications of automation in mHealth

mHealth function	Application of automation
------------------	---------------------------

REACH people in need	Identify clients when they are in need of support
Deliver EFFECTIVE intervention	Standardize intervention delivery
	Adapt intervention to client status & response
REDUCE BURDEN on HCW	Reduce manual message review & triage
	Prompt, guide or compose HCW messages

[figure not shown]
NLP refers to methods that transform and represent natural language for computation.^{25,26} Used in ubiquitous tools such as internet searching and email spam filtering, NLP is receiving growing attention in biomedical fields as a way to harness large quantities of rich, free text data, which are prohibitively resource-intensive to manually summarize.²⁷⁻²⁹ Essentially, NLP breaks a piece of text (a *corpus*) into its constituent *tokens* (typically words) and represents each token numerically. Many approaches have

been developed for numerical representation. They range from representing each word type as an arbitrary integer and summarizing the corpus by word frequencies, to representing each word as a multidimensional vector of *features*.³⁰ Features can be assigned based on expert linguistic knowledge, for example a categorical variable indicating parts of speech or root word.^{25,26} Recently, machine learning algorithms have been developed for *contextual word embedding* – feature definition based on a word’s distribution in other corpora, on the grounds that words found in similar contexts have similar meanings.³¹⁻³³ These algorithms have been shown to have excellent performance as predictors in a variety of classification tasks,³⁰ but the features they identify are generally not interpretable by humans.

Machine learning (ML) methods can be used to predict clinical outcomes based on natural language.

ML refers to computer algorithms that derive parameters of mathematical models by iteratively learning from observed data.^{34,35} ML can be supervised, meaning *labeled* data with linked predictor and outcome values are available to train the model; or unsupervised, meaning data are unlabeled and the algorithm clusters similar data together without considering outcome. ML methods can be used in analysis of unstructured natural language such as SMS messages in several ways. As described above, unsupervised ML models known as *neural networks* can be used to generate feature vectors from text.³⁰ Additionally, feature vectors generated by (ML or non-ML) NLP can in turn be used as predictors in supervised ML tasks such as classifying whether text indicates a particular health outcome (**Fig. 2**).

Figure. 2. Use of NLP & ML for SMS analysis t=time

[figure not shown]
b. Experience and preliminary work. Briefly describe experience or preliminary work or data (if any) that you, your team, or your collaborators/co-investigators have that supports the feasibility and/or safety of this study.

It is not necessary to summarize all discussion that has led to the development of the study protocol. The IRB is interested only in short summaries about experiences or preliminary work that suggest the study is feasible and that risks are reasonable relative to the benefits. Examples: Your team has already conducted a Phase 1 study of an experimental drug which supports the Phase 2 study being proposed in this application; your team has already done a small pilot study showing that the reading skills intervention described in this application is feasible in an after-school program with classroom aides; your team has experience with the type of surgery that is required to implant the study device; the study coordinator is experienced in working with subjects who have significant cognitive impairment.

We have developed NLP models with promising performance for detection of urgent client messages.

Using 1497 messages sent by the 30 most active participants in the Mobile WACH NEO pilot study, we developed NLP models using message metadata, word frequencies and contextual word embeddings to detect clinical urgency of messages. **Fig. 3** displays precision-recall curves summarizing performance of 6 representative models using a variety of linguistic features and modeling approaches. To evaluate potential clinical usefulness of models, we identified two potential model applications and associated evaluation criteria. A “triage” model rules out messages by identifying with very high recall (sensitivity) the messages of interest (i.e. urgent messages) for healthcare workers to focus their review on, while significantly reducing the number of messages reviewed. A “prioritize” model identifies messages of interest with very high precision (positive predictive value), allowing healthcare workers to read those messages first, while still reading the remaining messages later. Each ideal model occupies a region on the precision-recall plot; a model whose precision-recall curve falls in one of the two regions would be a candidate model for pilot testing. To date, we have developed one model close to the “triage” region. We are continuing to optimize model performance and are optimistic we can achieve further performance gains.

Figure 3. Precision-recall curves for urgency models

The ongoing Mobile WACH NEO RCT presents an opportunity to evaluate feasibility and performance of NLP models in practice

While model performance relative to a known label can be summarized using variables such as precision and recall, the utility of NLP for improving efficiency of nurse workflow must be determined empirically. We therefore propose to conduct a pilot study in which we compare nurse workflows when using the conventional Mobile WACH platform vs. workflows when using an NLP-enabled Mobile WACH platform. An ongoing RCT, Mobile WACH NEO, is evaluating use of the Mobile WACH platform to support neonatal health in Nairobi and Western Kenya. In this proposal, we will compare workflow in the context of the Mobile WACH NEO RCT with workflow in an NLP-enabled variant of the same intervention (named AI-NEO).

1.9 Supplements. Check all boxes that apply, to identify relevant Supplements that should be completed and uploaded to **Zipline**.

This section is here instead of at the end of the form to reduce the risk of duplicating information in this IRB Protocol form that you will need to provide in these Supplements.

Check all That Apply	Type of Research	Supplement Name
	Department of Defense The research involves Department of Defense funding, facilities, data, or personnel.	SUPPLEMENT Department of Defense
	Department of Energy The research involves Department of Energy funding, facilities, data, or personnel.	SUPPLEMENT Department of Energy

	Drug, biologic, botanical, supplement Procedures involve the use of any drug, biologic, botanical or supplement, even if the item is not the focus of the proposed research	SUPPLEMENT Drugs
	Emergency exception to informed consent Research that requires this special consent waiver for research involving more than minimal risk	SUPPLEMENT Exception from Informed Consent for Emergency Research (EFIC)
	Genomic data sharing Genomic data are being collected and will be deposited in an external database (such as the NIH dbGaP database) for sharing with other researchers, and the UW is being asked to provide the required certification or to ensure that the consent forms can be certified	SUPPLEMENT Genomic Data Sharing
	Medical device Procedures involve the use of any medical device, even if the device is not the focus of the proposed research, except when the device is FDA-approved and is being used through a clinical facility in the manner for which it is approved	SUPPLEMENT Devices
	Multi-site or collaborative study The UW IRB is being asked to review on behalf of one or more non-UW institutions in a multi-site or collaborative study.	SUPPLEMENT Multi-site or Collaborative Research
	Non-UW Individual Investigators The UW IRB is being asked to review on behalf of one or more non-UW individuals who are not affiliated with another organization for the purpose of the research.	SUPPLEMENT Non-UW Individual Investigators
	Other REDCap Installation Attestation for Electronic Consent The research will use a non-UW installation of REDCap for conducting and/or documenting informed consent.	SUPPLEMENT Other REDCap Installation
	None of the above	

1.10 Confirm by checking the box below that you will comply with the COVID requirements described on HSD's [COVID webpage](#), which are based on the location of the in-person study procedures and the vaccination status of study team members and study participants.

Review the HSD website for current guidelines about which in-person research activities are allowable.

Confirmed

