5 PROCEDURES

- 5.1 Study procedures.** Using lay language, provide a complete description of the study procedures, including the sequence, intervention or manipulation (if any), drug dosing information (if any), blood volumes and frequency of draws (if any), use of records, time required, and setting/location. If it is available: Upload a study flow sheet or table to **Zipline**.

For studies comparing standards of care: It is important to accurately identify the research procedures. See UW IRB [POLICY Risks of Harm from Standard Care](#) and the draft guidance from the federal Office of Human Research Protections, [“Guidance on Disclosing Reasonably Foreseeable Risks in Research Evaluating Standards of Care”](#); October 20, 2014. Information about pediatric blood volume and frequency of draws that would qualify for expedited review can be found in this [reference table](#) on the Seattle Children’s IRB website.

Aim 1 – model validation

Nurses will self-administer an electronic tablet-based questionnaire that will present them with a series of participant messages and ask them to categorize each message’s urgency according to a provided definition. The questionnaire will also include open-ended questions to enter comments on each assessment. No identifiable information will be collected.

Aim 2 – interface design

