5.4 Data variables. Describe the specific data that will be obtained (including a description of the most sensitive items). Alternatively, a list of the data variables may be uploaded to **Zipline**.

See attached data collection instruments:

- Aim 1 validation questionnaire
- Aim 2 FGD guide
- Aim 3 pregnant client screening questionnaire
- Aim 3 pregnant client enrollment questionnaire

- Aim 3 pregnant client follow-up questionnaire
- Aim 3 pregnant client variables for data abstraction
- Aim 3 pregnant client verbal autopsy questionnaire
- Aim 3 nurse IDI guide

5.5 Data sources. For all types of data that will be accessed or collected for this research: Identify whether the data are being obtained from the subjects (or subjects' specimens) or whether they are being obtained from some other source (and identify the source).

If you have already provided this information in Question 5.1, you do not need to repeat the information here.

The data will be obtained from subjects' self-report and from their clinic based medical record.

5.6 Identifiability of data and specimens. Answer these questions carefully and completely. This will allow HSD to accurately determine the type of review that is required and the relevant compliance requirements. Review the following definitions before answering the questions:

Access means to view or perceive data, but not to possess or record it. See, in contrast, the definition of "obtain".

Identifiable means that the identity of an individual is or may be readily (1) ascertained by the researcher or any other member of the study team from specific data variables or from a combination of data variables, or (2) associated with the information.

Direct identifiers are direct links between a subject and data/specimens. Examples include (but are not limited to): name, date of birth, medical record number, email or IP address, pathology or surgery accession number, student number, or a collection of data that is (when taken together) identifiable.

Indirect identifiers are information that links between direct identifiers and data/specimens. Examples: a subject code or pseudonym.

Key refers to a single place where direct identifiers and indirect identifiers are linked together so that, for example, coded data can be identified as relating to a specific person. Example: a master list that contains the data code and the identifiers linked to the codes.

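### Sections 1.5 and 5.1 give nurses different Aim 1 tasks; under 1.5 the nurse reference label is not independent of the models it ranks

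*Protocol*

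**What the plan says.** Section 1.5, Aim 1: ten nurses are shown client messages "annotated with urgency predictions from the top 3 best performing NLP models". "Each nurse will be asked to report their agreement with each prediction". The selection rule follows: "The model with the highest sensitivity and specificity compared with the nurse" reference standard goes into the Mobile WACH system.

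Section 5.1, Aim 1: a tablet questionnaire "will present them with a series of participant messages and ask them to categorize each" one by urgency, using a supplied definition, with room for comments. It mentions neither model predictions nor agreement ratings.

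The form's own prompts bear on which section governs. The prompt to 1.5 says "You will be asked to describe the specific procedures in a later section". The prompt to 5.1 asks the applicant to "provide a complete description of the study procedures". The instrument, "Aim 1 validation questionnaire", is listed in section 5.4 as an attachment and is not part of the text available.

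Section 1.8 b sets out regions of the precision-recall plot; a model whose curve falls in one of them "would be a candidate model for pilot testing".

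**The concern.** Rating agreement with a displayed prediction and classifying a message from a definition are different measurements. The first elicits the reference label with the index tests in view. A nurse who is unsure and goes along with a wrong prediction turns that model's error into a correct call.

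- If each prediction is rated separately, every accepted error raises the model's apparent sensitivity and specificity. A model with more errors has more to gain.
- If the nurse settles on one label per message and the predictions sway it, models that err together can gain and a model that dissents from them can lose.

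The choice of model is the stated output of Aim 1 and fixes what the Aim 3 pilot runs. The bias cannot be removed in analysis: once a nurse has seen the predictions for a message, her unprompted label for it is lost.

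**Working it through.** **Text comparison**

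| | Section 1.5 | Section 5.1 |
|---|---|---|
| Shown to nurse | Message plus three predictions | Message |
| Response | Agreement with each prediction | Urgency category |
| Basis | The prediction | A supplied definition |
| Order of items, masking | Not stated | Not stated |

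A form that takes the category first and agreement second would satisfy both, but neither section says so.

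**Size.** There is no Aim 1 figure to reproduce. Every input below is an assumption: 5, 10 or 20% of messages urgent, and 5, 10, 20 or 30% of wrong predictions accepted. At 0% acceptance there is no bias.

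*(a) Each prediction rated separately.* Let p be the share urgent, s and c the sensitivity and specificity against an unprompted nurse, and a the share of wrong predictions accepted.

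- TP = ps + a(1−p)(1−c)
- FN = (1−a)p(1−s)
- TN = (1−p)c + ap(1−s)
- FP = (1−a)(1−p)(1−c)

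Worked case: p = 0.10, a = 0.20, A = 0.80/0.92, B = 0.78/0.80 (sensitivity/specificity).

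- A sensitivity: TP = 0.080 + 0.0144 = 0.0944; FN = 0.0160; 0.0944/0.1104 = 0.855
- B sensitivity: TP = 0.078 + 0.0360 = 0.1140; FN = 0.0176; 0.1140/0.1316 = 0.866
- A specificity: TN = 0.828 + 0.0040 = 0.8320; FP = 0.0576; 0.8320/0.8896 = 0.935
- B specificity: TN = 0.720 + 0.0044 = 0.7244; FP = 0.1440; 0.7244/0.8684 = 0.834

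Four pairs in which A truly leads on both measures, at the same p and a:

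| True A v B | Apparent A v B |
|---|---|
| 0.80/0.92 v 0.78/0.80 | 0.855/0.935 v 0.866/0.834 |
| 0.80/0.92 v 0.78/0.90 | 0.855/0.935 v 0.845/0.919 |
| 0.85/0.92 v 0.80/0.85 | 0.892/0.935 v 0.870/0.877 |
| 0.95/0.75 v 0.93/0.70 | 0.972/0.790 v 0.963/0.745 |

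Over all 48 combinations (4 pairs × 3 values of p × 4 values of a), A's lead shrinks on both measures in all 48. It reverses on sensitivity in 8, all in the first pair, which has the 12-point specificity gap. It never reverses on specificity.

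*(b) One shared label.* With probability 1−a the label is the unprompted one; otherwise it is the majority of the three predictions. A = 0.80/0.92; B and C = 0.78/0.90; C copies B with probability q.

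Worked case by exact enumeration: p = 0.10, q = 0.25, a = 0.10.

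- Urgent messages: P(B and C both flag) = 0.78(0.25 + 0.75×0.78) = 0.6513; P(B and C differ) = 0.2574; P(majority flags) = 0.6513 + 0.80×0.2574 = 0.8572
- Non-urgent messages: 0.10(0.25 + 0.75×0.10) = 0.0325; 0.1350; 0.0325 + 0.08×0.1350 = 0.0433
- Labelled urgent: 0.0900 + 0.10(0.10×0.8572 + 0.90×0.0433) = 0.1025
- Of these, flagged by A: 0.0720 + 0.10(0.10×0.7270 + 0.90×0.0134) = 0.0805, giving 0.785
- Of these, flagged by B: 0.0702 + 0.10(0.10×0.7543 + 0.90×0.0379) = 0.0812, giving 0.792

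Apparent sensitivity, A v B, with 10% urgent:

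| B–C copying | a = 0.05 | a = 0.10 | a = 0.20 |
|---|---|---|---|
| 0% | 0.801 v 0.782 | 0.802 v 0.784 | 0.803 v 0.788 |
| 25% | 0.793 v 0.786 | 0.785 v 0.792 | 0.771 v 0.803 |
| 50% | 0.785 v 0.790 | 0.770 v 0.800 | 0.741 v 0.818 |

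A keeps its specificity lead throughout this table. With independent errors A keeps both leads up to a = 0.30 at each prevalence. At 20% urgent and 25% copying, the sensitivity reversal appears only from a = 0.20 (0.791 v 0.800).

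**The case against.** The bias arises only if 1.5 is followed, and 1.5 is a lay summary of aims whose prompt defers procedures to a later section. Section 5.1, meant to be complete, describes an ordinary classification task, and under it no dependence is shown. The questionnaire that would settle the matter is not visible. All of this stands and limits the finding to a certain conflict of text with a conditional bias.

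The illustrations can also be challenged.

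- Separate ratings fit poorly if three flags are shown together, since a nurse cannot sensibly agree with both urgent and not urgent. This is fair, and it makes the shared-label version the more natural one.
- If the rule means the highest sum of sensitivity and specificity, A stays ahead in all 48 separate-rating cases. That is correct, but it does not carry over to the shared label. At 10% urgent, 25% B–C copying and a = 0.10, A still leads on the sum (0.785 + 0.920 v 0.792 + 0.903). At a = 0.20 it does not (0.771 + 0.921 v 0.803 + 0.907).
- Letting only B and C share errors is the structure least kind to A. If all three share errors, at 10% urgent, A keeps both leads through a = 0.20 with 25% sharing and through a = 0.10 with 50% sharing. Reversal becomes less likely but remains possible.

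Finally, the candidates have already been screened, section 1.8 b reports earlier precision-recall work on 1,497 messages, and Aim 3 tests workflow directly. A poor choice among close candidates is a modest harm in a pilot. That bears on weight; it does not reconcile the two tasks.

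**Conclusion.** The point holds. Sections 1.5 and 5.1 describe different tasks and the text does not reconcile them. If 5.1 is intended, 1.5 is wrong. If 1.5 is intended, 5.1 is incomplete and the reference is not independent of the models. If a two-step form is intended, neither section says so.

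Neither the direction nor the size of any effect on the ranking can be estimated from the protocol. Under the assumed inputs it runs from nothing, through a smaller lead for the better model, to a changed order on sensitivity. A changed order needs either a large specificity gap with separate ratings or correlated model errors with a shared label. The matter should be corrected before Aim 1 begins. Confidence is medium, because the unseen questionnaire may already take the label first.

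**What to change.** Bring 1.5 into line with 5.1. State that each nurse labels every message from the supplied definition with no prediction on screen, that all three models are scored against that label, and that any agreement rating is asked only once the label is locked and is not used as the reference.

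This takes one sentence in 1.5, one clause in 5.1 and, if the tablet form now shows predictions first, a change of screen order. The nurses and messages are unchanged. The only burden is a slightly longer questionnaire if agreement ratings are kept as a second step.
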